#### Table 6.4. Treatment-Emergent Adverse Event Analysis Periods

Abbreviations: AE = adverse event; IP = investigational product; N/A = not applicable/available; PT = Preferred Term; SAE = Serious Adverse Event; SOC = System Organ Class; TEAE = treatment-emergent adverse event.

#### 6.12.3. Deaths

The listing of all deaths by patient for all enrolled patients will be provided as part of the SAE listing, regardless of the investigator's or the sponsor's judgment about causality. Each listing will include study ID, investigator ID, patient ID, treatment group, baseline age, sex, associated AE, first and last dose date for open label insulin lispro and randomized IP, and the event date.

#### 6.12.4. Hypoglycemic Events and Other Adverse Events

The analysis plans for the following adverse events are discussed in Section 6.12.4.1 through Section 6.12.4.4:

- hypoglycemic events
- systemic hypersensitivity reaction
- injection site reaction
- hepatobiliary events

These AE analyses will be similar to the TEAE analyses. Refer to Table 6.4 for the requirement of analysis data for a specific analysis period.

#### 6.12.4.1. Hypoglycemic Events

Hypoglycemia events that occur during the study outside the MMTT will be captured starting from Visit 2 through Visit 801. Whenever hypoglycemia is suspected, the patient should record the blood glucose value, any associated symptoms, and the treatment administered in patient diary. A set of events is counted as 1 event in analysis if it consists of an originating event and subsequent continuing events as marked by the patient in paper diary, or the duration between adjacent events

is  $\leq$ 30 minutes. The event with the highest severity will be selected for analysis with severity determined in the order of: 1) it is a severe hypoglycemia, 2) it has symptoms of hypoglycemia reported, and 3) it has the lowest blood glucose value. If there are multiple events tied in all 3 aspects, the event with the largest number of non-missing responses to the questions of nocturnal hypoglycemia and postmeal time frame will be selected. If there are still multiple events tied, the latest event (based on data entry time) will be selected.

The following types of hypoglycemia events will be derived in the analysis data sets: documented hypoglycemia, severe hypoglycemia, nocturnal hypoglycemia (documented and occurring between bedtime and waking), probable symptomatic hypoglycemia, and overall hypoglycemia. Only severe hypoglycemia will be collected as AEs and all episodes of severe hypoglycemia will be considered as SAEs. Documented hypoglycemia (including documented symptomatic hypoglycemia, documented asymptomatic hypoglycemia and documented unspecified hypoglycemia) will be based on blood glucose (BG)  $\leq$ 70 mg/dL. In addition, documented clinically significant hypoglycemia with similar criterion as above documented hypoglycemia except for the threshold of BG <54 mg/dL will be summarized.

Table 6.5 provides detailed statistical methods for each endpoint related to hypoglycemia. For these analyses, hypoglycemia events prior to discontinuation of IP will be summarized. Additional analyses for other types of hypoglycemic events not mentioned in the table and for the post-treatment period may be conducted as needed.

The incidence and number of episodes of hypoglycemia (regardless of the type of hypoglycemia event) during the MMTT will be summarized by treatment and time relative to the meal ( $\leq 0.5$ ,  $\leq 1$ ,  $\leq 2$ ,  $\leq 4$ , >1 to  $\leq 2$  and >2 to  $\leq 4$  hours after start of the meal) and analyzed by Fisher's exact test.

A listing of patients with at least 1 severe hypoglycemia reported (as SAE) after randomization will be provided. Summary of severe hypoglycemia treatment and outcome from the patient diary will be provided.

A list of MedDRA PTs will be used for the narrow search of potential severe hypoglycemia in spontaneously reported AEs. The events identified through the search strategy that are also reported as SAEs will be summarized and compared between treatments. Fisher's exact test will be used to assess the treatment difference in the proportion of patients with potential severe hypoglycemia.

Analysis Period	Statistical Method
0-12, 0-26, 12-26weeks	Negative binomial regression with
	treatment, and log (exposure/30
	days for exposure/365.25 days) as
	the offset in the model.

 Table 6.5.
 Summary of Analyses for Endpoints Related to Hypoglycemia

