9.4. Safety

9.4.1. Hypoglycemia

Patients are encouraged to perform SMBG, whenever hypoglycemia may be suspected, either by symptoms experienced or perceived increased risk as related to dietary intake, physical activity, or inadvertent or atypical insulin dosing. All patients will be instructed to treat a BG \leq 70 mg/dL (3.9 mmol/L) as hypoglycemia.

Hypoglycemia events will be collected in the patient diaries provided by the sponsor via the investigator. If a hypoglycemia event is suspected, the patient should record the BG value, any associated symptoms, and the treatment administered in the patient diary. The patient should contact the site as necessary. Reports of hypoglycemia will be classified by the investigator as "severe" or "not severe" based upon data collected in the patient diary and in consultation with the patient; see below and Section 9.2.1. All episodes of severe hypoglycemia must be collected as AEs via electronic data entry and reported as SAEs.

Hypoglycemia will be described using the following definitions:

Documented Glucose Alert Level, BG ≤ 70 mg/dL (3.9 mmol/L)

- **Documented symptomatic hypoglycemia:** with typical symptoms of hypoglycemia.
- **Documented asymptomatic hypoglycemia:** without typical symptoms of hypoglycemia.
- **Documented unspecified hypoglycemia**: with no information about symptoms of hypoglycemia available.

Documented Clinically Significant Hypoglycemia with similar criterion as above except for threshold BG <54 mg/dL (3.0 mmol/L)

- Documented symptomatic hypoglycemia
- Documented asymptomatic hypoglycemia
- Documented unspecified hypoglycemia

Severe hypoglycemia

• Severe hypoglycemia (in adults): Patients had altered mental status, and could not assist in their own care, or were semiconscious or unconscious, or experienced coma with or without seizures, and the assistance of another person was to actively administer carbohydrate, glucagon, or other resuscitative actions. Plasma glucose measurements may not be available during such an event, but neurological recovery attributable to the restoration of BG concentration to normal is considered sufficient evidence that the event was induced by a low BG concentration (BG ≤70 mg/dL [3.9 mmol/L]).

Other hypoglycemia:

- **Nocturnal hypoglycemia:** Any documented hypoglycemic event (including severe hypoglycemia) that occurs between bedtime and waking.

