- **Relative hypoglycemia:** An event during which typical symptoms of hypoglycemia occur, that does not require the assistance of another person and is accompanied by BG >70 mg/dL (3.9 mmol/L).
- **Probable symptomatic hypoglycemia:** Symptoms of hypoglycemia were present, but BG measurement was not reported.
- Overall hypoglycemia: This optional category combines most cases of hypoglycemia (documented hypoglycemia and probable symptomatic hypoglycemia, including severe hypoglycemia). It does not include relative hypoglycemia. Nocturnal and severe hypoglycemia are special cases of documented or probable hypoglycemia. If an event of hypoglycemia falls into multiple subcategories, that event should only be counted once in the category of overall hypoglycemia.

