**Objectives and Endpoints** 

Objectives	Endpoints
Other Secondary Objectives (continued)	
6. To compare LY900014 and insulin lispro with respect to the incidence and rate of documented symptomatic postmeal hypoglycemia	
 
6. Rate (events/patient/year and/or events/patient/30 days) and incidence (percent of patients with at least 1 event) of documented symptomatic postmeal hypoglycemia within 1 and 2 hours after start of a meal from Week 12 through Week 26, Week 0 through Week 26
 

 
To compare LY900014 and insulin lispro with respect to the incidence and rate of documented symptomatic hypoglycemia
 
	
 
Rate (events/patient/year and/or events/patient/30 days) and incidence (percern of patients with at least 1 events) of documented symptomatic hypoglycemic events from Week 12 through Week 26, Wee 0 through Week 26
 

8. To compare LY900014 and insulin lispro with respect to 1,5-AG	
 
Change from baseline 1,5-AG values at Week 26
 

9. To compare LY900014, and insulin lispro with respect to 10-point SMBG profiles	
 
Change from baseline 10-point SMBG values at Week 26
 

10. To compare LY900014 and insulin lispro with respect to total, basal, and prandial insulin dose	
 
Change from baseline in total, basal and prandial insulin doses and prandial/total insulin dose ratios at Week 26
 

 
To compare LY900014 and insulin lispro with respect to the proportion of patients achieving HbA1c targets
 
	
 
The proportion of patients with HbA1c <7% and ≤6.5% at Week 26
 

Certiary/Exploratory Objectives	
12. To compare the safety of LY900014 and insulin lispro	12. Adverse events, vital signs, chemistry, and hematology laboratory measures
13. To compare the incidence of treatment- emergent positive anti-insulin lispro antibodies for LY900014 and insulin lispro	13. Incidence of treatment-emergent positive ant insulin lispro antibodies

 
To compare LY900014 and insulin lispro with respect to quality of life as measured by the EQ-5D-5L
 
	
 
Change from baseline in EQ-5D-5L UK-population based health state index score and EQ-VAS score at Week 26
 

15. To compare LY900014 and insulin lispro with respect to diabetes treatment satisfaction as measured by the ITSQ	
 
Change from baseline in ITSQ regimen inconvenience and lifestyle flexibility domai scores at Week 26
 

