a All documented hypoglycemia and the subcategories based on the thresholds of blood glucose ≤70 mg/dL and blood glucose <54 mg/dL will be analyzed, all postmeal hypoglycemia based on the threshold of ≤70 mg/dL and <54 mg/dL will be applied.

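### The SAP classifies a merged hypoglycemia episode from one selected diary record, so an episode can lose its lowest glucose and drop out of the <54 mg/dL count

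*SAP*

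**What the plan says.** SAP 6.12.4.1 counts a set of records as one event when it consists of an originating event and "subsequent continuing events as marked by the patient in paper diary, or the duration between adjacent events" is at most 30 minutes. No time limit is stated for patient-marked continuations.

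From each set one record is taken: "The event with the highest severity will be selected for analysis with severity determined in the order of" severe status first, then "2) it has symptoms of hypoglycemia reported, and 3) it has the lowest blood glucose value". Remaining ties go to the record with more non-missing answers on nocturnal and postmeal timing, then to the latest entry.

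The analysed categories depend on glucose. Protocol 9.4.1 sets the first tier as "Documented Glucose Alert Level, BG ≤ 70 mg/dL (3.9 mmol/L") and the clinically significant tier at <54 mg/dL. Footnote a to SAP Table 6.5 says that all documented hypoglycemia and the "subcategories based on the thresholds of blood glucose ≤70 mg/dL and blood glucose <54 mg/dL will be analyzed". Under Protocol 9.4.1 a symptomatic record above 70 mg/dL is relative hypoglycemia and one without a glucose value is probable symptomatic hypoglycemia, so neither is documented. Of the overall category the protocol adds: "It does not include relative hypoglycemia".

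**The concern.** The rule picks a whole record. Neither document carries the set's lowest glucose, or a symptom reported on another record, over to the episode. The tie-break points the same way, since preferring the record with more complete timing answers matters only if those fields are read from the retained record.

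A glucose-defined tier can therefore be decided by a reading that is not the lowest in the episode. The <54 tier is the most exposed, and SAP version 2 added postmeal summaries at that threshold. The absolute rates and incidences in Table 6.5 are at stake: a patient whose only reading below 54 lies in such a set becomes a non-event at that tier.

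**Working it through.** The plan gives no figure to reproduce, so the check has two parts.

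**1. What the rule does to each kind of pair.** Inputs: the ranking in SAP 6.12.4.1 and the definitions in Protocol 9.4.1. There are six non-severe record types: asymptomatic <54, asymptomatic 54–70, symptomatic <54, symptomatic 54–70, symptomatic >70 (relative) and symptomatic with glucose missing (probable). They form 6 × 7 / 2 = 21 unordered pairs. Illustrative values are 50, 65, 80 and missing. A missing glucose is assumed to rank last on the third criterion, because the SAP does not say. Five pairs lose a threshold:

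| Pair in the set | Record kept | Class under the SAP | Threshold lost |
|---|---|---|---|
| asymptomatic 50 + symptomatic 65 | 65 | documented symptomatic, ≤70 only | <54 |
| asymptomatic 50 + symptomatic 80 | 80 | relative | <54 and ≤70 |
| asymptomatic 50 + symptomatic, missing | missing | probable | <54 and ≤70 |
| asymptomatic 65 + symptomatic 80 | 80 | relative | ≤70 |
| asymptomatic 65 + symptomatic, missing | missing | probable | ≤70 |

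So <54 is lost in 3 of 21 pair types and ≤70 in 4 of 21. The SAP does not say whether relative records enter the merging. If they are removed first, 5 × 6 / 2 = 15 pairs remain; 2 still lose <54, 2 still lose ≤70, and none leaves the overall category. These are counts of pair types, not frequencies. No pair loses a record that is itself documented symptomatic (0 of 21).

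**2. Possible size.** The documents give no glucose distribution, symptom pattern or share of multi-record episodes, so all inputs here are assumptions: first record symptomatic with glucose N(66, 9) mg/dL; recheck without symptoms, equal to the first value plus N(d, 10); share s of all episodes with such a second record, 10% to 30%. Let p₁ be the probability that the first value meets the threshold and pₘ the probability that the lower of the two does. The rule keeps the first record, so

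loss = s(pₘ − p₁) / [(1 − s)p₁ + s·pₘ].

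With d = 0:

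- **<54:** p₁ = Φ((54 − 66)/9) = 0.091 and simulated pₘ = 0.218. Within two-record episodes the loss is 0.127/0.218 = 58%. At s = 0.10 it is 0.0127/(0.0819 + 0.0218) = 12%. At s = 0.30 it is 0.0381/(0.0637 + 0.0654) = 30%.
- **≤70:** p₁ = Φ((70 − 66)/9) = 0.672 and simulated pₘ = 0.770. Within two-record episodes the loss is 0.098/0.770 = 13%. At s = 0.10 it is 0.0098/(0.6048 + 0.0770) = 1.4%. At s = 0.30 it is 0.0294/(0.4704 + 0.2310) = 4.2%.

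Other recheck assumptions, at s = 10% to 30%:

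| Recheck | Loss of <54 | Loss of ≤70 |
|---|---|---|
| d = 0, none symptomatic | 12–30% | 1.4–4.2% |
| d = +10, none symptomatic | 2.6–7.5% | 0.4–1.1% |
| d = +10, half symptomatic | 1.3–3.8% | 0.2–0.5% |
| d = +20, none symptomatic | 0.3–0.8% | 0–0.1% |

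In this model every first record has a glucose value, so the ≤70 losses arise only where that value exceeds 70 (1 − 0.672 = 33% of first records). They apply only if relative records are merged.

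**The case against.** Ranking symptoms above glucose has a purpose. When only one record is kept, it protects documented symptomatic hypoglycemia, which is a named secondary endpoint. With glucose ranked first, a lower asymptomatic record would displace the symptomatic one. The enumeration bears this out, and <54 is not named in the Table 4.1 objectives. This stands as a defence of the order. It does not explain why the thresholds should be read from one record.

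Four stronger readings are tempting, and the documents do not support them.

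- **The secondary endpoint is clearly undercounted.** It is affected only where symptoms and the low value sit on different records. Such a set contains no record that meets the definition by itself.
- **Episodes vanish altogether.** Leaving even the overall category requires a relative record to be merged and selected, and the SAP is silent on whether these enter. A severe record without glucose can displace a documented value, but that episode is still counted as severe and overall.
- **Early postmeal events are pushed into later windows.** Endpoint 6 concerns the rate and incidence "of documented symptomatic postmeal hypoglycemia within 1 and 2 hours after start of a meal". Where two symptomatic records straddle the 1-hour limit, lowest glucose does decide which is kept. Timing by onset or by lowest value is a design choice.
- **The treatment comparison is biased.** The trial is double-blind and the rule is the same in both arms. Nothing in the documents shows that such sets are more common in one arm.

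The size is also open to challenge. Patients are told to treat values of 70 or below, so rechecks may often be higher, which favours the lower rows of the second table.

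**Conclusion.** The point holds as a defect in a counting rule. Read as written, SAP 6.12.4.1 removes from the <54 tier any merged episode whose sub-54 values all lie on records without reported symptoms, when a symptomatic record in the set has a glucose of 54 or more or missing. It also removes documented ≤70 status when the selected record has no glucose or, if relative records are merged, one above 70. Where all records are symptomatic with glucose recorded and none is severe, the lowest value is kept correctly.

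The direction is certain: an undercount, mainly at <54. The size is not. The illustrative range for <54 runs from 0.3% to about 30% and rests wholly on assumed recheck behaviour and an assumed share of multi-record episodes. The effect is on reported absolute rates and incidences; no between-arm bias is shown.

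**What to change.** In SAP 6.12.4.1, keep the merging rule, the one-event count, and the selected record as the source of the nocturnal and postmeal fields. Add that the ≤70 and <54 mg/dL thresholds apply to the lowest glucose recorded in the merged set, that the episode is symptomatic if any record in the set reports symptoms, and that it is severe if any record is severe. State also whether records above 70 mg/dL enter the merging.

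Among the 21 pair types this changes only the five in the first table. All become documented symptomatic, and the three that contain a 50 also count at <54.

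The cost is a short text change and a small derivation change using fields already collected. There are two downsides. Symptoms and lowest glucose may come from different records of one episode, which matters most for patient-marked continuations because they have no time limit. Reported <54 rates may also rise slightly in both arms.

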#### **I8B-MC-ITSD Statistical Analysis Plan Version 2**

Endpoint	Analysis Period	Statistical Method
Incidence of hypoglycemic events All Documented a Nocturnal a Documented Symptomatic a Non-Nocturnal (or Daytime) (Documented and between waking and bedtime) a	0-12, 0-26, 12-26 weeks	Logistic regression with treatment as an independent variable.
Rate of postmeal hypoglycemic events (per patient per 30 days / year) for all 3 main meals Documented Symptomatic a	$\leq 0.5, \leq 1, \leq 2, \leq 4, >1$ to $\leq 2, >2$ to $\leq 4$ and >4 hours after start of a meal within 0-12, 12-26, 0-26 weeks	Negative binomial regression with treatment, and log (exposure/30 days or exposure/365.25 days) as the offset in the model.
Incidence of postmeal hypoglycemic events for all 3 main meals Documented Symptomatic a	$\leq 0.5, \leq 1, \leq 2, \leq 4, >1$ to $\leq 2, >2$ to $\leq 4$ and >4 hours after start of a meal within 0-12,12-26, 0-26 weeks	Logistic regression with treatment as an independent variable.
Rate of severe hypoglycemic events (per patient per year / 100 years)	0-12, 0-26, 12-26 weeks	Exposure adjusted rate per year / 100 years (calculated by total number of events divided by total exposure for individual patients) will be provided and the empirical method (see 0 for details) will be used for treatment comparison.

Endpoint	Analysis Period	Statistical Method
Incidence of severe hypoglycemic	0-12, 0-26, 12-26 weeks	Proportion of patients with severe
events		hypoglycemia will be reported. The
		treatment comparison will be based on
		a logistic regression model with
		treatment as an independent variable.
Rate of postmeal severe	$\leq 0.5, \leq 1, \leq 2, \leq 4, >1$ to $\leq 2, >2$	Due to limit data for the rare event,
hypoglycemic events (per patient per	to $\leq$ 4 and $>$ 4 hours after start of	only summary statistics will be
year / 100 years) for all 3 main meals	a meal within 0-12,12-26, 0-26	provided by treatment. No statistical
	weeks	comparison will be conducted.
Incidence of postmeal severe	$\leq 0.5, \leq 1, \leq 2, \leq 4, >1$ to $\leq 2, >2$	Fisher exact test will be used for
hypoglycemic events for all 3 main	to $\leq$ 4 and $>$ 4 hours after start of	treatment comparison.
meals	a meal within 0-12, 12-26, 0-	
	26weeks	

Summary of Analyses for Endpoints Related to Hypoglycemia

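### The SAP's nocturnal hypoglycemia rule needs a glucose value and omits the protocol's severe-event clause, so severe night-time events without a reading fall outside the nocturnal analysis

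*SAP*

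**What the plan says.** SAP 6.12.4.1 lists the event types to be derived. One of them is "nocturnal hypoglycemia (documented and occurring between bedtime and waking". Severe events are not mentioned in that definition. The same section ties the documented category to a glucose value: the sentence naming its three subtypes runs "documented unspecified hypoglycemia) will be based on blood glucose (BG" and then gives the limit of 70 mg/dL or below. A second analysis uses a limit of below 54 mg/dL. Table 6.5 names nocturnal events in its incidence row and adds a daytime counterpart, "Non-Nocturnal (or Daytime) (Documented and between waking and bedtime".

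Protocol 9.4.1 defines nocturnal hypoglycemia as "Any documented hypoglycemic event (including severe hypoglycemia) that occurs between bedtime and waking". Its definition of severe hypoglycemia says "Plasma glucose measurements may not be available during such an event" and that "neurological recovery attributable to the restoration of BG concentration to normal is considered sufficient evidence" of a low BG, which it specifies as 70 mg/dL or below. Under overall hypoglycemia it adds: "Nocturnal and severe hypoglycemia are special cases of documented or probable hypoglycemia". Probable symptomatic hypoglycemia is the category in which "Symptoms of hypoglycemia were present, but BG measurement was not reported".

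**The concern.** The protocol's definition carries a clause on severe events that the SAP's derivation rule lacks. A programmer following the SAP would test for a BG value first, and a severe event without one would fail that test whatever its time of day. The nocturnal table would then omit some severe night-time events, and its counts would not match the protocol's safety category. No other row of Table 6.5 fills the gap, because severe events are split there by time since a meal and not by night and day.

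**Working it through.** The point turns on definitions. The plan states no figure to reproduce.

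**Step 1. Classify night-time severe events under each text.**

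| Severe event at night | SAP 6.12.4.1 | Protocol, reading (a) | Protocol, reading (b) |
|---|---|---|---|
| BG 70 mg/dL or below recorded | nocturnal | nocturnal | nocturnal |
| No BG recorded | not nocturnal | nocturnal | not nocturnal |

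Reading (a) takes the protocol's bracket to add all severe events to the documented ones. Reading (b) takes it to say only that some documented events are severe. The texts diverge in one cell, and only under (a).

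**Step 2. Choose between the readings.** Three features of protocol 9.4.1 favor (a).
- Under (b) the bracket adds nothing, since a severe event with a qualifying reading is already documented.
- The severe definition provides for a missing reading and accepts neurological recovery as evidence of BG at or below 70 mg/dL.
- Nocturnal and severe events are placed under documented or probable hypoglycemia, and probable events have no BG value. The SAP makes nocturnal a subset of documented only.

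None of these says outright that a severe night-time event without a reading is nocturnal. Reading (a) is the better inference.

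**Step 3. See whether the SAP's merging rule matters.** SAP 6.12.4.1 merges entries no more than 30 minutes apart and keeps one record, ranking severe status ahead of the lowest glucose. If the severe entry has no BG and its neighbor has a qualifying one, the record kept is the severe one. The SAP does not say whether it takes over the neighbor's value. Read literally, that episode could also drop out.

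**Step 4. Gauge the size.** The documents give no severe or nocturnal rates and no share of severe events without a reading, so this is illustration only. From the protocol: 350 randomized patients and 26 weeks, about 0.5 year. Assumed: 95% of that time on treatment, 5 to 20 severe events per 100 patient-years, 30 to 50% of them at night, and 25 to 50% of those without BG.

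- Exposure: 350 × 0.5 × 0.95 = 166 patient-years
- Severe events: 166 × 0.05 = 8 to 166 × 0.20 = 33
- Share at night without BG: 0.30 × 0.25 = 0.075 to 0.50 × 0.50 = 0.25
- Events left out, from unrounded values: 8.3 × 0.075 = 0.6 to 33.25 × 0.25 = 8.3

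If nocturnal events at 70 mg/dL or below ran at 5 per patient-year (also assumed), there would be about 831, and 8.3/831 = 1.0%. The upper end puts all the assumptions on severe events at their extremes together. Incidence moves less readily than the event count: a patient is lost from it only if every qualifying night-time event in the period lacked a reading.

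**The case against.** The strongest reply is that the protocol's own definition opens with documented events, and documented is headed by a BG limit. On reading (b) the SAP is a fair paraphrase. The sentence on documented or probable hypoglycemia also sits inside the definition of an optional overall category. Taken at full strength, it would bring in non-severe probable night-time events as well, which nobody proposes. This shows that the protocol is not explicit. It does not explain why the bracket is there, and it leaves the SAP applying the narrower reading without saying so.

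Several stronger conclusions are tempting but unsupported.
- *That the most serious night-time events are lost from the safety analysis.* Severe events with a qualifying BG still count as nocturnal. All severe events remain in the severe rate and incidence (Table 6.5), the patient listing and the narratives.
- *That these events belong in the nocturnal table below 54 mg/dL.* The protocol's recovery rule is evidence of 70 mg/dL or below and no lower.
- *That the daytime category breaks a protocol rule.* The protocol defines no daytime category; it is the SAP's own.
- *That the SAP's silence in its revision history shows an undeclared change.* That list covers the main changes from version 1 to version 2, and nothing shows that this wording was different in version 1.
- *That the nocturnal rate is certainly affected.* Only the incidence row legibly names nocturnal events; the endpoint label of the first rate row is not legible in the available text.

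**Conclusion.** The point holds in a limited form. As written, the SAP rule excludes severe night-time events without a BG value from nocturnal incidence, and from the rate if that row covers nocturnal events. The protocol's better reading includes them. This is a stated derivation rule that can give a different count from the protocol's category, so it is more than a missing detail.

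The effect is small. On the assumptions above it runs from under one event to about eight, with a handful at most the likely outcome. Nocturnal hypoglycemia is not a listed objective or endpoint in protocol Table ITSD.1 or SAP Table 4.1. The primary and multiplicity-adjusted tests and the listed secondary endpoints, including severe hypoglycemia, are unaffected. There is no basis in the documents for inferring a bias between the arms. The conclusion rests on reading (a) of the protocol. A reader who prefers (b) should still want the SAP to state which rule it applies.

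**What to change.** In SAP 6.12.4.1, define nocturnal hypoglycemia as any documented event (BG 70 mg/dL or below), or any severe event with or without a BG value, that falls between going to bed and waking. State that severe events without BG count in the 70 mg/dL nocturnal analysis only, not in the one below 54 mg/dL.

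For consistency the same rule can be applied to the daytime category in Table 6.5. Add a table footnote that the nocturnal and daytime categories may contain severe events not counted in the row for all documented events; otherwise the rows will appear not to reconcile.

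The cost is a sentence or two in the SAP, one footnote and a small change to the derivation program. No new data are needed.
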